## 6.4 Blinding

### 6.4.1 Blinding of the Examiner

This is an open-label study, however, in order to avoid potential involuntary bias of the examiner by the smoking status, he/she will be kept blinded to the patient arm after randomization. In order to enforce the blinding, the examiner will wear a prescribed mask to avoid noticing the odor, during the full periodontal examination at 3 and 6 months. The blinded examiner should avoid contact with the patient outside of the required full periodontal examinations. In addition, the patients will be asked to wash their hands. If the examiner should become unblinded for any reason, including accidental disclosure, the unblinding event will be documented by the Investigator in a specific log kept in the Site Investigator File. A patient-specific unblinding event will not lead to discontinuation of the patient and will not prevent the use of the patient's data, including those recorded after disclosure.

If a designee needs to perform the periodontal assessments, he/she needs to have been trained on the PD and CAL probing before doing it, *i.e.*, by an examiner who attended the calibration session (section 10.2.1). This needs to be described in the back-up plan that will be provided by the sites (section 10.2.1). The blinding status of the designee will be described in the specific log for blinding.

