### 7.3.5 Dental Assessments

In the investigational sites with two or more dentists, a dentist will measure each periodontal disease parameter. In the investigational sites with one dentist only, a dentist will preferably measure these parameters, however, a trained hygienist could also do it.

From the moment the examiner meets the patient, blinding of the smoking status should be ensured, as described in section 6.4.1.

A single examiner at each site will perform all measurements throughout the whole study duration, if possible. A calibration session between examiners from different sites must be organized before V1.

Each site will need to develop a plan on how to ensure that they have properly qualified personnel, including back-up personnel necessary to conduct the required dental assessments. This will be documented in the delegation of authority log.

Unified periodontal probes will be used to ensure that all examiners will apply the same pressure when probing. The probe in this study will be PCPUNC15 (#30) by Hu-Friedy. Measurements will be rounded to the nearest millimeter (mm), based on visual judgement.

The dental assessments listed in the sections 7.3.5.1 to 7.3.5.8 below will be recorded on the prescribed periodontal charts.

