### 7.6.2 Scaling and Root Planing (SRP)

First SRP will be performed on teeth with PD  $\geq 4$  mm by using Gracey Hand Curettes at V2. The following SRP treatments will be performed and recorded as “unscheduled” SRP visits. SRP treatments of teeth with PD  $< 4$  mm will be performed based on PI’s judgment, at the time he/she finds it necessary. All SRP treatments must be completed within 8 weeks after V2. If additional SRP visits need to be performed because of periodontitis worsening, based on Investigator’s judgement, they will be recorded as unscheduled visits, including the reason for this unplanned SRP.

PD, mobility and BOP before SRP will be measured as per the standard of care treatments at V2. These data will, however, not be reported in the CRF.

The order of SRP should be determined for individual patients. The identification of each tooth treated and the respective time of treatment should be recorded.

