## 12 PLANNED STATISTICAL METHODS

### 12.1 General Considerations

Full details of the statistical analysis will be given in the Statistical Analysis Plan (SAP). Any changes to the planned statistical methods will be documented in the CSR. The statistical evaluation will be performed using SAS®, version 9.2 or later.

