### Confidentiality Statement

Data and information contained in this document are considered to constitute trade secrets and confidential commercial information, and the legal protections provided to such trade secrets and confidential information are hereby claimed under the applicable provisions of applicable law. No part of this document may be publicly disclosed without the written consent of Philip Morris Products S.A.

- a. The informed consent process can be started as soon as the patient is invited to participate in the study, but the ICF must be signed no later than before the first assessment at V1.
- b. IQOS starter kit (*i.e.*, device and a selection of *HeatStick* flavor variants available on the Japanese market) will be delivered to all patients randomized to the IQOS arm. They will start using it as soon as possible.
- c. The Investigator or study collaborator will collect the completed diaries at V3 and V4, and the diary data will be transcribed into the CRF. The questionnaire can be filled before or after V3, but because V4 is the last Visit, the questionnaire for Month 6 must be filled before or at V4, regardless of the time when the previous questionnaire was filled.
- d. Sex, date of birth, ethnicity.
- e. Prior medication taken within 3 months prior to V1.
- f. The same spot urine collection will be used for pregnancy (all females) and cotinine tests, and for NEQ, CEMA, total NNAL and creatinine measurements (BoExp). Sampling for BoExp should be performed as soon as possible, and samples frozen immediately.
- g. These tubes will be discarded at the end of the visit if the patient is not enrolled.
- h. Full periodontal examination consists in the measurement of PD, CAL and BOP on 6 sites per tooth, tooth mobility, plaque control record and gingival inflammation of the target teeth. At V1, full periodontal examination should be the last assessment performed as part of the eligibility criteria, to avoid unnecessary examination for those patients who are in any case not eligible.
- i. Will not be recorded in the case report form.
- j. Additional SRP treatments will be performed during “unscheduled” visits and will be completed within 8 weeks after initial treatment.
- k. From V2 to V4, patients will be asked not to drink, eat, chew gum, use mouth rinse or brush their teeth for at least 30 minutes before collection of oral samples (*i.e.*, SP, GCF or buccal swabs).

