9.5.1.1 Primary Analyses

Primary Analysis of Change from Baseline in PD at V4	
Population	
 • As Exposed Set For this analysis, subjects categorized in IQOS user, cigarette user or dual user will be included with initial PD \geq 4mm will be included.
	The primary analysis will be performed on the As Exposed Set using a mixed model for repeated measurements (MMRM). Estimates of difference in PD will be calculated for Cigarette User against IQOS User categories and Cigarette User against Dual User categories. The model will include the PD change from baseline as the dependent variable, adjusting for the following covariates; 
 1. Daily cigarette consumption at V1 2. Disease severity at V1 3. Full mouth PD at V1 4. Visit 5. Product use pattern (IQOS user, cigarette smoker or dual user) 6. Interaction between visit and product use

Confidentiality Statement

Data and information contained in this document are considered to constitute trade secrets and confidential commercial information, and the legal protections provided to such trade secrets and confidential information are hereby claimed under the provisions of applicable law. No part of this document may be publicly disclosed without the written consent of Philip Morris Products S.A

Primary Analysis of Change from Baseline in PD at V4

7. Average daily cigarette use at each visit
8. Interaction between Daily cigarette consumption at V1 and product use
9. Interaction between Disease severity at V1 and product use
10. Time since last SRP
11. Number of target tooth/teeth extracted
12. Number of non-measured target tooth/teeth extracted
13. Baseline tooth mobility

Site will be included as a random effect. The degrees of freedom will be adjusted by using Kenward Roger (KR) method. A Toeplitz structure (“type=toep”) will be specified as the covariance matrix. However, other covariance structures may be used in case of non-convergence. Covariates 8-12 will be assessed for adequacy in the model using a step-wise (backward) approach through the following algorithm.

1. Fit a full model using maximum likelihood with all covariates
2. Perform a likelihood ratio test for the full model and drop the covariate with the largest p-value for the likelihood ratio statistic if it is more than 0.05.
3. Drop one covariate (only covariates 7-14) and re-fit the model.

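### The primary pocket-depth model adjusts for time since last SRP, an undefined post-randomization covariate that SRP given for worsening may reset

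*SAP*

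**What the plan says.** SAP 9.5.1.1 fits a repeated-measures model to PD change at V3 and V4. Item 10 of its covariate list is "Time since last SRP". SAP section 5 and 9.1.4 do not say which session counts, to which visit the time runs, or whether SRP for worsening counts. Item 10 lies in both ranges named for backward elimination (8 to 12 and 7 to 14), so it stays unless its likelihood-ratio p exceeds 0.05.

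The same model serves the FAS and PP analyses of PD (9.5.1.2) and the CAL analyses (9.5.2.1, 9.5.2.2). The primary model in protocol 12.6 has no SRP-timing term, and SAP section 7 does not list it as a change.

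On treatment, protocol 7.6.2 says "All SRP treatments must be completed within 8 weeks after V2". It then provides for a further case: "If additional SRP visits need to be performed because of periodontitis worsening". Such visits rest on the Investigator's judgement and are recorded as unscheduled, "including the reason for this unplanned SRP". Appendix 1, footnote j, says that additional SRP "will be completed within 8 weeks after initial treatment".

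**The concern.** SRP starts at V2 and continues at later visits, so this covariate is a post-randomization quantity. If SRP for worsening counts as the last SRP, a patient who responds badly is re-treated and then has a short time since last SRP. The model would condition the product comparison on a consequence of poor response. Selection adds to this, because the term is kept when it predicts PD.

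The confirmatory IQOS-versus-cigarette difference is at stake, and so is the FAS comparison by randomized arm, which carries the same term. The SAP sets no strategy for SRP given for worsening. It is therefore unclear whether the target is the effect with re-treatment as given or the effect without it. No planned table shows SRP for worsening by group, so a reader who saw the term retained could not easily judge what it had done.

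**Working it through.** **1. Does the 8-week limit cover SRP for worsening?** For: protocol 7.6.2 speaks of all SRP, and footnote j applies the limit to additional treatments. Against:
- The worsening sentence follows the limit, sets none of its own and treats such SRP as unplanned.
- Footnote j hangs on the schedule row for the first SRP. Protocol section 4 (unscheduled visits) describes additional visits as those needed to complete the SRP treatment.
- The first full re-examination is V3, day 90 ± 7 = 83 to 97, after day 56.
- Protocol 8.1.1 leaves treatment of unexpected worsening to the Investigator with no time limit.

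The text does not decide it, so both cases were simulated.

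**2. Design figure.** From protocol 12.2: one-sided alpha 0.025, power 80%, SD 0.5 mm, difference 0.25 mm. n = 2 × (0.5/0.25)² × (1.960 + 0.842)² = 62.8, so 63 by the normal approximation against 64 stated. 64/0.75 = 85.3, rounded up to the stated 86. SE of the difference = 0.5 × √(2/64) = 0.088 mm.

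**3. Simulation inputs.**
- From the documents: 64 per group, SD and difference as above, planned SRP ending day 0 to 56, V3 at day 83 to 97, V4 at day 166 to 194.
- Assumed: V3-V4 correlation 0.6, uniform timing, re-treatment in 5, 10 or 20% overall under one rule for both groups, benefit 0, 0.3 or 0.6 mm.
- Model: V3 and V4 fitted jointly by maximum likelihood, with the term kept if twice the log-likelihood gain exceeds 3.84.
- Shift = V4 difference after selection minus the V4 difference from the model without the term. Negative means toward no difference.

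**4. All SRP within 8 weeks.** With a trigger correlating 0.5 with V3 response and 0.3 with V4, the shift is -0.002 to +0.001 mm. Under a second set of settings, with the term always in and re-treatment late in the window in up to about 27% of cigarette and 14% of IQOS users, it is -0.002 to -0.017 mm for trigger correlations 0.3 to 0.75. It is -0.026 mm when timing is driven fully by the V3 value.

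**5. SRP for worsening possible after V3, V3-V4 correlation fitted.**
- Trigger close to the V4 state, no benefit: -0.012, -0.025 and -0.042 mm at 5, 10 and 20%. The term is kept in 61, 87 and 98% of runs, and power falls from 80% to 77, 73 and 68%.
- Trigger equally related to V3 and V4, no benefit: -0.005, -0.012 and -0.026 mm.
- Trigger is V3 PD: 0.000 mm with no benefit; +0.010, +0.026 and +0.050 mm with benefit 0.6 mm.

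The largest shift is 0.050/0.088 = 0.57 SE. One-sided type I error is 2.0%, against 2.2% without the term.

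**6. The same with the sample code as printed.** The repeated statement in SAP 9.5.1.1 nests visit within subject as its subject effect. Each record is then its own block and no V3-V4 correlation is fitted. At 20% re-treated:

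| Trigger | Benefit (mm) | Correlation fitted | Code as printed |
|---|---|---|---|
| Close to V4 state | 0 | -0.042 | -0.059 |
| V3 PD | 0 | 0.000 | -0.043 |
| V3 PD | 0.3 | +0.019 | -0.011 |
| V3 PD | 0.6 | +0.050 | +0.002 |

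**7. Is the shift bias?** With no benefit, the effects with and without re-treatment coincide at 0.25 mm. At 20% the model without the term gives 0.250 and the model with it 0.207 (trigger close to V4), so the shift is bias. With benefit 0.6 mm and a V3 trigger, the estimates are 0.166 without and 0.217 with the term. That moves toward the effect without re-treatment, so whether it is bias depends on the target.

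**8. Planned-course definition.** Counting days from the last planned SRP, with no reset for worsening, gives a shift of 0.000 mm in the settings tested and type I error 2.2%.

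**The case against.** The strongest reply is that both sentences that set a limit set it at 8 weeks, and SRP after V3 is inferred from silence. That is fair. Under the limit the effect ranges from negligible to small, though it is not zero if timing follows response.

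Healing time is also a plausible prognostic factor: at V3 it can run from 83 - 56 = 27 to 97 - 0 = 97 days. Dropping the term is therefore not the only remedy; a proper definition would do. This stands.

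The range of shifts also depends on the covariance. With the code as printed the upward shift all but disappears. The SAP text names a Toeplitz structure, so the code may be a slip, but a claim of bias in either direction cannot be made without that condition. The simulation also leaves out site, dual users and the other covariates, so its retention rates are not those of the full elimination procedure.

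Four stronger readings are tempting:
- **The term raises the false-positive risk for IQOS.** This appeared only when IQOS users were assumed to be re-treated more often regardless of response (overall 10%, no benefit). Ratios of 1.5, 2 and 4 took type I error from 2.2% to 3.0, 3.9 and 5.6%. Nothing in the documents suggests such a ratio.
- **Re-treatment is decided by someone who knows the arm.** Protocol 6.4.1 blinds only the examiner and says "The blinded examiner should avoid contact with the patient outside of the required full periodontal examinations". At single-dentist sites, though, "In the investigational sites with one dentist only, a dentist will preferably measure these parameters", so the treating dentist may also be the blinded examiner. The documents do not show how often the two roles are separate.
- **The absence from protocol 12.6 is itself a breach.** Protocol 12.1 says "Full details of the statistical analysis will be given in the Statistical Analysis Plan (SAP", so the omission is secondary.
- **The reader would see nothing.** Outputs 15.4.5.2 and 15.4.5.3 give the coefficients and the dropped variables, and listing 15.3.7.8 covers periodontal treatment. Only the by-group summary is missing.

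**Conclusion.** The concern holds in a limited form. Item 10 is a post-randomization term with no derivation in the confirmatory PD model and the FAS, PP and CAL models. Read literally, it can carry a consequence of poor response.

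If the 8-week limit covers SRP for worsening, the shift is negligible to about -0.03 mm. If it does not, it is about -0.04 to +0.05 mm with a V3-V4 correlation fitted. With the code as printed it is mostly toward no difference, about -0.06 to 0 mm. Larger assumptions give more: benefits of up to 1.0 mm gave at most +0.11 mm.

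Every size rests on assumed rates, benefits and correlations, because the documents give none of them. Under one re-treatment rule for both groups the cost is a distorted estimate and, in some settings, lost power. It is not a raised type I error. The point should be corrected, but it does not by itself undermine the trial's conclusion.

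**What to change.** Take item 10 out of the primary PD and CAL models (SAP 9.5.1.1, 9.5.2.1) and their FAS and PP versions (9.5.1.2, 9.5.2.2), and use it only in a supportive sensitivity model. If it stays, define it as days from the last planned-course SRP (within 8 weeks of V2) to the visit, not reset by SRP recorded for worsening. Use that definition in 9.5.3 too if the term remains there.

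Add a table of SRP for worsening by randomized arm and exposure group, as a stated exception to the 9.1.6 rule that keeps unscheduled-visit data out of tables.

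The cost is SAP wording, one table and at most one derived variable from SRP dates and reasons already recorded. Nothing changes for patients. Dropping a healing-time covariate may lose a little precision. The change deals with this term only: items 7, 11 and 12 are also post-randomization and need their own decision.

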## **6.7 Concomitant Therapeutic Procedures**

Any concomitant therapeutic procedure (e.g. tooth extraction due to cavity or due to worsening of periodontitis, appendicectomy), which is not part of study procedures (as described in Section 7), will be fully documented in the source document and transcribed into the CRF. All medications used during these concomitant procedures will also be captured in the source document and reported as concomitant medication in the CRF.

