## 12.6 Primary Analysis

The primary analysis evaluates the change from baseline in PD, which will be calculated for each patient across all sites with a baseline PD  $\geq 4$  mm, resulting in one value per patient per endpoint for each visit (baseline, Month 3 and 6).

The primary analysis will be performed on the As Exposed Set using a mixed model for repeated measurements (MMRM) for only subjects who have used cigarettes and/or Heatsticks. The model will include the PD change from baseline as the dependent variable, adjusting for daily cigarette consumption and disease severity at V1, full mouth PD at V1, exposure group and its interaction with visit. Site will be included as a random effect. The modeling assumptions will be evaluated and the model fit will be assessed by the analysis of the residual (diagnostics) and by comparing the values predicted vs. the observed values (calibration).

Additionally, the analysis will be performed on the FAS, PP and Adherent Use populations as a supportive sensitivity analysis. Additional sub group analyses such as for “Other” product use groups may be analyzed and will be defined in the SAP.

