Periodontal assessment	Full mouth assessment of PD, CAL, BOP, tooth mobility, PCR, and assessment of gingival inflammation of the target teeth.
Randomization	After all assessments of V1 have been completed, patients will be randomized to IQOS or cigarette arm. Patients will be informed of their randomized study arm by the study site during V2. All patients will be instructed to continue to solely use their assigned product until they complete the study.
Safety follow-up	After the day of Discharge at V4, patients will enter into a 7-day safety follow-up for the recording of spontaneously reported new AEs/SAEs and the follow-up of ongoing AEs/SAEs by the study site.
Screen failure	Patient who signs ICF but was not enrolled. Re-screening of patients who did not meet any entry criteria will not be permitted.
Target site	The site of a target tooth, preferably the deepest of the tooth, from which the GCF will be collected.
Target tooth	At V1, for all eligible patients, the Investigator or designee will designate 4 target teeth, i.e. , preferably one per quadrant. Teeth with PD \geq 5 mm but < 7 mm will be preferably selected. If their location does not correspond to one per quadrant, the Investigator or designee will designate the target teeth preferably as single-rooted, and distributed as evenly as possible. Target teeth identification will be reported in the CRF.

Confidentiality Statement

Data and information contained in this document are considered to constitute trade secrets and confidential commercial information, and the legal protections provided to such trade secrets and confidential information are hereby claimed under the provisions of applicable law. No part of this document may be publicly disclosed without the written consent of Philip Morris Products S.A

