9.5.3 Exploratory Analyses

Summary Table of Exploratory Analysis to Evaluate the Change in (i) Multiplex assay (MAP) (ii) Parallel Reaction Monitoring (PRM)

Population	:	
 As Exposed Set
Contents	:	
The analysis will be performed on the As Exposed Set using a mixed model for repeated measurements (MMRM).
 
The model will include the log change from baseline as the dependent variable, adjusting for the following covariates;
 
 Daily cigarette consumption Disease severity at V1 MAP/ PRM at V2 Visit Product use Interaction between visit and product use Interaction between Daily cigarette consumption at V1 and product use Average daily cigarette use at each visit Interaction between Disease severity at V1 and product use Time since last SRP Number of target tooth/teeth extracted Number of non-measured target tooth/teeth extracted Baseline tooth mobility Site will be included as a random effect. The degrees of freedom will be adjusted by using Kenward Roger (KR) method. A Toeplitz structure (“type=toep”) will be specified as the covariance matrix. However, other covariance structures may be used in case of non-convergence. Covariates 7-12 will be assessed for adequacy in the model using a step-wise (backward) approach through the following algorithm. 
 Fit a full model using maximum likelihood with all covariates Perform a likelihood ratio test for the full model and drop the

Confidentiality Statement

Data and information contained in this document are considered to constitute trade secrets and confidential commercial information, and the legal protections provided to such trade secrets and confidential information are hereby claimed under the provisions of applicable law. No part of this document may be publicly disclosed without the written consent of Philip Morris Products S.A

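### The primary PD model can adjust for teeth extracted after randomisation; one count covers only the four target teeth and the other is undefined

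*SAP*

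**What the plan says.** **Primary model.** SAP 9.5.1.1 lists 13 covariates for the mixed model of PD change. Number 11 counts target teeth extracted. Number 12 is the "Number of non-measured target tooth/teeth extracted", a term defined nowhere in either document.

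**Selection.** Both start in the full model and may be dropped: "Covariates 8-12 will be assessed for adequacy in the model using a step-wise (backward) approach". A term goes if its likelihood-ratio p-value exceeds 0.05. Step 3 of the same algorithm gives another range, "Drop one covariate (only covariates 7-14) and re-fit the model", in a list that ends at 13. Covariates 11 and 12 are open to elimination under either range.

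**Target teeth.** SAP 2.1.1: "At V1, for all eligible patients, the Investigator or designee will designate 4 target teeth". Depths of at least 5 mm and below 7 mm are preferred. Protocol 7.3.5.2 and 7.5.4 use these teeth for gingival crevicular fluid (GCF) and plaque sampling.

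**Reasons for extraction.** Protocol 6.7 gives as an example "tooth extraction due to cavity or due to worsening of periodontitis". Protocol 8.1.1 adds dental conditions not due to periodontitis, such as a broken tooth.

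**Protocol model.** Protocol 12.6 specifies a model "adjusting for daily cigarette consumption and disease severity at V1, full mouth PD at V1, exposure group and its interaction with visit", with site as a random effect. It has no extraction term. SAP section 7 reports only the changes to the As Exposed Set and the removal of the Adherent Use Set.

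**Reach.** The model is reused for PD at 3 months and for CAL (SAP 9.5.2.1), and for the FAS and Per Protocol analyses (9.5.1.2, 9.5.2.2). The GCF models in 9.5.3 also carry "Number of target tooth/teeth extracted" and its companion.

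**The concern.** A covariate measured after randomisation is harmless only if neither the product nor the response to treatment affects it. An extraction count does not clearly pass that test, because worsening periodontitis is one of the causes the protocol names. When the count is a consequence of poor response, adjusting for it compares the groups as if they had lost equal numbers of teeth, and part of the difference under test can be removed. This touches the product-use contrast in the As Exposed Set. It also touches the FAS contrast, which is by randomised arm and is the one place where randomisation would otherwise protect the comparison. No inferential PD or CAL analysis is planned without these candidate terms.

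If the aim was to allow for tooth loss in the endpoint, covariate 11 does so incompletely. It counts four designated teeth, while the endpoint uses every site with initial PD of at least 4 mm. The documents also do not say how an extracted tooth enters PD change. SAP 9.1.4 covers teeth with fewer than four recorded sites, and Protocol 12.6 asks for one value per patient per visit without saying whether it is a mean of site changes or a difference of visit means.

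**Working it through.** **1. The plan's own sample size.** Inputs from Protocol 12.2: difference 0.25 mm, SD 0.5 mm, one-sided 2.5%, power 80%. The normal approximation gives n = 2 × (1.960 + 0.842)² × 0.5² / 0.25² = 62.8, so 63 per group. The noncentral t gives 64 (power 0.801). Then 64 / (1 − 0.25) = 85.3, so 86 per arm and 172 in total. The stated figures reproduce, and no covariate enters them.

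**2. Timing.** Target teeth are designated at V1. SAP 4.3.1 places randomisation after the V1 assessments; Protocol 9.2 shows it at V2, 7 to 14 days after V1. Apart from that short gap, any extraction of a target tooth is post-randomisation.

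**3. Coverage by covariate 11.** Eligibility needs at least 15 natural teeth and more than 30% of them with PD of at least 4 mm (Protocol 5.1.1, criteria 5 and 6). The fewest diseased teeth is the smallest whole number above 0.30 × teeth.

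| Teeth | 0.30 × teeth | Fewest diseased | Four target teeth as a share |
|---|---|---|---|
| 15 | 4.5 | 5 | 80% |
| 20 | 6.0 | 7 | 57% |
| 24 | 7.2 | 8 | 50% |
| 28 | 8.4 | 9 | 44% |

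Every eligible patient therefore has at least one endpoint tooth that covariate 11 cannot count.

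**4. Size of the shift.** The documents give no extraction rates, so what follows is an illustration. Each row has 2,000 simulated trials with 64 per group, a true difference of 0.25 mm and SD 0.5 mm. A latent healing score u has correlation r with the residual PD response. Extractions per patient are Poisson with mean (group rate) × exp(−u − 0.5), capped at 4. The exponential factor averages 1, so the group rate is the mean count. The term is tested by likelihood ratio and kept if p ≤ 0.05.

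| Mean extractions, cigarette / IQOS | r | Unadjusted (mm) | Term always in (mm) | Term kept if p ≤ 0.05 (mm) | Kept in |
|---|---|---|---|---|---|
| 0.05 / 0.05 | 0.5 | 0.251 | 0.251 | 0.251 | 23% |
| 0.05 / 0.05 | 0.8 | 0.248 | 0.249 | 0.249 | 48% |
| 0.10 / 0.05 | 0.5 | 0.251 | 0.240 | 0.245 | 30% |
| 0.10 / 0.05 | 0.8 | 0.249 | 0.233 | 0.236 | 62% |
| 0.20 / 0.10 | 0.5 | 0.249 | 0.230 | 0.235 | 49% |
| 0.20 / 0.10 | 0.8 | 0.251 | 0.221 | 0.222 | 86% |
| 0.30 / 0.10 | 0.5 | 0.250 | 0.214 | 0.223 | 54% |
| 0.30 / 0.10 | 0.8 | 0.252 | 0.194 | 0.196 | 92% |

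With r = 0, at all four pairs of rates, the difference stays at 0.251 to 0.255 mm and the term is kept in 5 to 6% of trials.

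**5. Why the table looks like this.** In least squares, adjusted difference = unadjusted difference − b × (mean extractions in IQOS − mean extractions in cigarette), where b is the slope of response on extractions within groups. In the last row the shift is 0.252 − 0.194 = 0.058 mm for a gap of 0.10 − 0.30 = −0.20, so b is about −0.29 mm per tooth. A shift needs both a non-zero slope and a gap between groups, and its sign follows which group loses more teeth. The p ≤ 0.05 rule tests the slope, so it discards the term mainly when the term is harmless.

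**The case against.** Several points against this are fair.

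- **The adjustment is conditional.** Either covariate may be eliminated, and Table 15.4.5.3 will list what was dropped. In the milder rows the term goes in most trials. This stands as a limit on frequency, but the rule keeps the term more often as extraction becomes more closely tied to healing.
- **Extraction is not the same as treatment failure.** A reader might infer that it is. The protocol also names cavity and broken tooth, and the eligibility criteria admit patients who already have teeth needing extraction at V1. The supportable statement is that extraction can follow from poor response and that the count does not separate reasons.
- **Target teeth are not foreign to the endpoint.** With a preferred depth of 5 mm or more they are normally a subset of the endpoint teeth. The fault is the endpoint teeth left uncounted.
- **Covariate 12 may have been meant for the other teeth.** Its wording does not settle this. The four-tooth limit is certain for covariate 11 and only the literal reading of covariate 12. An undefined term in a primary model is still a defect.
- **The harm is small and need not favour the sponsor.** In a separate simulation where extraction depends on product only through response (rates again assumed), one-sided rejection under no effect stayed at 2.4 to 2.7%. Power was 74 to 80%, against about 80.5% unadjusted. That stands for that mechanism.
- **The primary contrast is by actual use anyway.** Covariate 7, cigarette use at each visit, is a more direct post-randomisation adjustment. True, but the FAS model inherits the extraction terms as well.

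**Conclusion.** The point holds in a limited form. Two extraction counts outside the protocol model, and missing from the SAP's list of changes, are candidates in the primary PD model and in every PD and CAL model that inherits it. When extraction is related to healing they tend to be kept, and the contrast is then conditioned on a possible consequence of response. Covariate 11 never covers all endpoint teeth; covariate 12 is undefined.

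The size cannot be computed from the documents. Under the assumed rates, with the term always in the model, there is no shift if extraction is balanced or unrelated to healing. With the stronger link to healing (r = 0.8), the shift is 0.251 − 0.221 = 0.030 mm at 0.20/0.10 extractions per patient and 0.058 mm at 0.30/0.10. These are 12% and 23% of 0.25 mm, towards a smaller IQOS difference because cigarette users were assumed to lose more teeth.

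A reader might go further and call the direction unpredictable, since losing a deep tooth can raise the observed mean reduction. The documents do not support that as a finding. It depends on whether change is averaged over sites or taken between visit means, which Protocol 12.6 leaves open, and it was not calculated here. Nor do the documents show that the primary result will be biased. They show that the plan permits it without any evident gain.

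**What to change.** 1. Remove covariates 11 and 12 from the primary PD model and from the models that inherit it: PD at 3 months, CAL, and the FAS and Per Protocol versions.
2. If adjustment for tooth loss is wanted, define both counts over all endpoint teeth, split by reason for extraction, and confine them to a labelled sensitivity analysis.
3. State how an extracted tooth enters PD change. One option is site-level change averaged over the baseline sites of at least 4 mm that are still present, applied identically in both groups.
4. Add a table of extractions of all teeth, with reason, by randomised arm and by product-use group. No table in SAP 13.1.1 is titled for this.
5. In the GCF models of SAP 9.5.3 the post-randomisation concern is the same and the terms should be reconsidered. The coverage objection does not apply there, because GCF is taken from sites on the target teeth.
6. Record any covariate retained beyond Protocol 12.6 in SAP section 7, and give one elimination range that matches the list.

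The cost is two deleted covariates, one endpoint rule and one descriptive table. The sample size stays at 172.
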